#### **9.4 Days + 1 and + 2**

The following procedures will be performed on Days 1 and 2 post fulvestrant administration. Assessment by phone is allowed.

- Collection of concomitant medications
- Adverse event evaluations

#### **9.5 Day +7 ± 2 (Day 5 to 9)**

The following procedures will be performed on Day 7 post fulvestrant administration:

- Vital signs (blood pressure, pulse, respirations, temperature)
- PK - Plasma Fulvestrant Level
- Pain assessment (See Section 9.10)
- Collection of concomitant medications
- Adverse Event Evaluations

#### **9.6 Pre-Operative (Day 14 + 7) (Day 14 to 21)**

The following procedures will be done prior to surgery:

- ECOG performance status (Appendix 20.1)
- Vital signs (blood pressure, pulse, respirations, temperature)
- Digital tumor imaging
- PK - Plasma Fulvestrant Level
- Complete blood count with differential and platelet counts (includes hemoglobin, hematocrit, platelets and white blood cell count with differential)
- Chemistry panel (Includes Na+, K+, BUN/Urea, serum Cr, Glu, Alb, AST, ALT, Tbili)
- Pain Assessment (See Appendix 20.2)
- Concomitant Medications
- Adverse Events Evaluation
- Pregnancy test (for women of child-bearing potential)

#### **9.7 Day of Surgery (DOS) Day 14 to 45**

No study related procedures will take place during surgery. The surgeon will make every effort to maintain the bio-occlusive dressing and nipple markers in the mastectomy specimen unless surgical approach would be compromised. These markers are critical for pathological handling and processing of the mastectomy specimen to determine any effect of drug on treated and untreated ducts.

Upon complete removal of the mastectomy specimen, colored hydrogels (approximately 1 to 2ccs) will be injected into the previously treated ducts to allowed focused pathology assessment. It will then be sent to pathology for histological examination and tissue sample collection. Information regarding pathological assessment is in Section 10.1, Histological Assessment. For lumpectomy, this will not be feasible.

#### **9.8 Post-Operative/Pre-Discharge (DOS to DOS+D/C)**

Subjects will be assessed according to institutional policy after mastectomy or lumpectomy. In addition, subjects will be assessed for AEs, ECOG performance status (Appendix A), and vital signs (pulse, blood pressure, respiratory rate, temperature) recorded. In addition, as

noted above, blood will be drawn to assess organ function.

Subjects experiencing any adverse events prior to discharge which may have been caused by the study or the study drug, may stay longer in the hospital if indicated or may continue to be contacted by their doctor and study doctor. This will be recorded on the CRF.

In the absence of unresolved AEs that require follow-up after discharge, subject participation in this trial will end upon discharge from the hospital.

The following procedures will be performed post-surgery and before discharge:

- Vital signs (blood pressure, pulse, respirations, temperature)
- Concomitant Medications (collection of anesthesia, fluid support or post-surgical pain management is not required)
- Adverse Event Evaluation
- Clinical Breast Assessment
- Pathological Assessment

### **9.9 Subject Early Discontinuation**

Subjects who discontinue after any fulvestrant administration on Day 0 will complete the following procedures.

- Concomitant Medications
- Adverse Events Evaluation
- Reason(s) for discontinuation
- Pregnancy test (for woman of child-bearing potential)

If a subject is withdrawn or discontinues study participation, reasonable efforts will be made to complete the final study procedures. The subject will continue to be followed and medically managed in accordance with the arrangement that was in place prior to study enrollment.

**Table 2: Schedule of Assessments**

Timeline	Baseline	Fulvestrant Administration	Post Administration		Pre-Op	Day of Surgery	Day of Discharge 	Early Discontinuation
	Day							
Procedures	-14 to -1	0	1 and 2	7 (±2)	14 - 21	DOS (Day 14 to 45)	DOS +	Post fulvestrant administratio
Informed Consent	X							
Registration	X							
Physical Exam	X				X			
Medical History	X							
ECOG Performance Status	X				X			
Vital Signs 	X	X 		X	X		X	
Digital tumor imaging if needed	X				X			
PK - Plasma Fulvestrant Level		X 		X	X			
CBC with Diff & Platelets 	X				X			
Chemistry panel 	X				X			
Pregnancy Test 	X	X			X			X
Pain Assessment		X 		X	X			
Fulvestrant administration		X						
Concomitant Medications	X	X	X 	X	X		X 	X 
Adverse Event Evaluation		X 	X 	X	X		X	X 
Clinical Breast Assessment	X						X	
Pathological Assessment 	X						X	
Reason(s) for Discontinuation								X

1 Blood pressure, pulse, respiration, temperature

2 Prior to fulvestrant administration

3 On Day 0/fulvestrant administration, PK plasma samples are obtained pre-fulvestrant administration, and 4.5 hours post administration (see Table 1)

4 Includes hemoglobin, hematocrit, platelets and white blood cell count with differential

5 Includes Na+, K+, BUN/Urea, serum Cr, Glu, Alb, AST, ALT, Tbili

6 On Day 0/fulvestrant administration Pain Assessment completed prior to fulvestrant administration/nipple preparation (Intraductal only), Post Nipple Anesthesia (Intraductal only), at completion of fulvestrant administration, 30 minute, 1 and 4.5 hours post administration. (see Section 9.10)

7 Assessment by phone is allowed

8 Collection of anesthesia, fluid support or post-surgical pain management is not required

9 Assess adverse events during fulvestrant administration, immediately after administration, at 30 minutes, 1 hour and 4 hours

10 Only women of childbearing potential are tested at baseline or thereafter

11 Includes tissue sample collection for fulvestrant concentration

12 Participation in the trial concludes upon discharge from the hospital

### 9.10 Supportive Care

No other anti-estrogen medication is allowed during the study, and no estrogen therapy within 30 days prior to fulvestrant administration. Otherwise, concomitant medications and therapies deemed necessary for the supportive care and safety of the subject are allowed, provided their use is documented in the medical records and CRF. Collection of anesthesia during surgery, fluid support or post-surgical pain management is not required. Supportive care is provided as guided by institutional standards of care.

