### 8.1 Selection Criteria

#### 8.1.1 Inclusion Criteria:

1. Female
2. 18 years of age or older
3. Scheduled to undergo mastectomy or lumpectomy for Invasive Breast Cancer (clinical stage 1 or 2, ER+ low-to intermediate-grade) or DCIS
4. Pathological diagnosis of Invasive Ductal Carcinoma or Ductal Carcinoma *in Situ* (DCIS) requiring mastectomy or lumpectomy (Mixed ductal and lobular carcinoma acceptable)
5. Estrogen Receptor positive biopsy, as determined from a biopsy specimen obtained no more than 3 months prior to entry
6. ECOG performance scale of 0-1 (Appendix A)
7. Adequate organ function as defined by the following criteria:
  - a. Absolute neutrophil count (ANC)  $\geq 1500/\mu\text{L}$
  - b. Platelets  $\geq 100,000/\mu\text{L}$
  - c. Hemoglobin  $\geq 9.0 \text{ g/dL}$
  - d. Creatinine  $\leq 2$  times upper limit of normal

- e. Bilirubin  $\leq$  2 times upper limit of normal
  - f. Transaminases (AST/SGOT and ALT/SGPT)  $\leq$  2.5 times upper limit of normal
8. Able to sign informed consent
  9. Willing to use effective contraception for at least 100 days post study drug administration if subject is pre-menopausal.

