#### **8.1.2 Exclusion Criteria:**

1. Concurrent treatment with another anti-estrogen
2. Presence of an active infection requiring systemic therapy.
3. The following conditions contra-indicating fulvestrant administration:
  - a. Subjects with bleeding diatheses, thrombocytopenia or current anticoagulant use (excluding aspirin and anti-inflammatories)
  - b. Subjects with a known hypersensitivity to fulvestrant or any of its formulation components including castor oil, alcohol, benzyl alcohol, and benzyl benzoate.
  - c. Severe hepatic impairment.
4. Prior surgery on the ipsilateral breast which interrupts communication of the ductal systems with the nipple
5. Prior radiation to the breast
6. Pregnant or lactating
7. Impaired cardiac function or history of cardiac problems of NYHA Class III and IV (Appendix C 20.4)
8. Poor nutritional state as indicated by a BMI below 20. -
9. Presence of serious infection not controlled with systemic therapy
10. History of allergies to Lidocaine or Novocain
11. Concurrent participation in an experimental drug study.

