### 9.2 Baseline Assessment (Day -14 to -1)

Prior to fulvestrant administration, each subject will undergo testing for baseline data collection. Any baseline tests performed within 2 weeks prior to study enrollment need not be repeated: those data will be considered adequate for baseline evaluation.

Baseline tests include all of the following:

- Registration
- Medical History
- ECOG performance Status
- Vital Sign (blood pressure, pulse, respirations, temperature)
- Digital tumor imaging if a recent digital image is not available
- Complete blood count with differential and platelet counts (includes hemoglobin, hematocrit, platelets and white blood cell count with differential)
- Chemistry panel (Includes Na+, K+, BUN/Urea, serum Cr, Glu, Alb, AST, ALT, Tbili)
- Pregnancy test (for women of childbearing potential/pre-menopausal)
- Concomitant Medications
- Clinical Breast Assessment
- Pathological Assessment

If any of these tests or examinations, reveal criteria rendering the subject ineligible, they will be excluded from the study. **All subjects must have at least 14-days between fulvestrant administration and surgery.**

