### **13.2 Sample Size and Statistical Analyses**

A total of 30 subjects who are undergoing mastectomy or lumpectomy will be included in this study: 6 will receive intramuscular, and 24 will receive intraductal fulvestrant. With respect to the sample size for the latter group with 24 subjects, it will be possible to detect an effect size of approximately 0.60 with 80% power and 0.69 with 90% power. Both of these are in the medium to large range according to Cohen's terminology and are based on the demonstration of a reduction in the Ki67 labeling index mean from baseline (diagnostic biopsy) to week 4 (surgically excised specimen) using a paired t-test. With these effect sizes and an anticipated 50% decline in the mean index, then the expectation would be a standard deviation in this reduction of about  $\pm 83.7\%$  for 80% power and  $\pm 72.3\%$  for 90% power.

The primary endpoint of this study is to assess safety and tolerability as measured by adverse events, subject pain assessment as well as signs of topical irritation seen on the excised specimen. In addition, the effect of the administration will be evaluated with respect to the change in Ki67 labeling index (primary efficacy endpoint) and changes in estrogen and progesterone receptor expression (secondary efficacy endpoints)

Descriptive statistics will be used to summarize the data (means/medians and standard deviations/interquartile ranges for quantitative data and proportions/percentages for categorical data such as adverse events), and numerically compare the groups with entry diagnoses of invasive ductal carcinoma and DCIS, respectively. In addition, the 6 study subjects who receive intramuscular fulvestrant will be qualitatively compared with the main study cohort of 24 subjects who receive intraductal fulvestrant.

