The primary analysis of the change in Ki67 labeling index will be compared between the two time points (baseline or time of diagnostic biopsy versus 4 weeks or time of the surgically excised specimen collection) using the paired t-test (assuming normality of the differences) or the Wilcoxon signed rank test if normality cannot be demonstrated or a transformation to normality using the Box-Cox family of power transformations cannot be used. A similar analysis will be employed to evaluate the secondary endpoint of changes in mean estrogen receptor and progesterone receptor expression. In addition, 95% confidence intervals for the mean difference for these variables between the two time points will be computed using the t-statistic or a rank statistic as required by the distribution of the study data.

The results for the efficacy endpoints will be compared in a descriptive fashion with those seen by Kuter et al (Kuter I, Gee JMW, Hegg R et al): Dose-dependent change in biomarkers during neoadjuvant endocrine therapy with fulvestrant: results from NEWEST, a randomized Phase II study. *Breast Cancer Res Treat* 133: 237-246, 2012.

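### The estrogen-free period is counted from dosing but baseline Ki67, ER and PgR come from the earlier diagnostic biopsy, so an effect of stopping estrogen can be credited to fulvestrant

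*Combined protocol and SAP*

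**What the plan says.** Four places in the protocol bear on this.

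- **Section 9.10 (Supportive Care)** allows "no estrogen therapy within 30 days prior to fulvestrant administration". The interval is anchored to dosing.
- **Section 8.1.1 (repeated in the Section 2.0 synopsis)** requires estrogen-receptor positivity "as determined from a biopsy specimen obtained no more than 3 months prior to entry".
- **Section 13.2** bases the power statement on a "reduction in the Ki67 labeling index mean from baseline (diagnostic biopsy) to week 4 (surgically excised specimen) using a paired t-test". It gives the time points of the Ki67 analysis as "baseline or time of diagnostic biopsy versus 4 weeks or time of the surgically excised specimen collection". ER and PgR changes get a similar analysis. Ki67 change is named the primary efficacy endpoint; safety and tolerability are the primary objective of the study.
- **Section 8.1.2** lists "Concurrent treatment with another anti-estrogen" as an exclusion. Estrogen therapy is not on the list.

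Section 7.0 describes a non-randomized study. Under Section 13.2 the six intramuscular subjects are compared with the intraductal cohort only qualitatively, and the cited neoadjuvant fulvestrant study only descriptively. No covariate, subgroup or sensitivity analysis by estrogen exposure is described. Section 13.0 says that a detailed SAP will be written before database lock.

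**The concern.** The estrogen-free interval protects the time of dosing. The efficacy analysis starts at the biopsy, which can be much earlier. A woman taking estrogen when biopsied, who then stops in time to satisfy Section 9.10, contributes an on-estrogen baseline and an off-estrogen surgical value. Her whole change enters the paired difference.

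Nothing in the design would separate the two causes. The intramuscular subjects also receive fulvestrant and use the same biopsy baseline, so they do not isolate the effect of stopping estrogen. If stopping estrogen lowers Ki67 in an ER-positive tumor, the error favors the hoped-for result. What is at stake is how far a fall in Ki67, or a change in ER or PgR, can be read as a fulvestrant effect.

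**Working it through.** **1. The plan's own figures.** Exact paired t-test power, n = 24 (23 degrees of freedom), two-sided alpha 0.05. Alpha is not stated with the power figures; 0.05 two-sided is assumed, consistent with the planned 95% intervals.

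- 80% power: d = 0.597, and 50/0.597 gives an SD of 83.7%.
- 90% power: d = 0.691, and 50/0.691 gives an SD of 72.3%.

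These match the stated 0.60, 0.69, 83.7% and 72.3%. The sample-size arithmetic is not in question.

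**2. The timing.** Three months is 90 to 92 days. Entry is assumed to fall in the baseline window, 1 to 14 days before dosing.

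- Longest biopsy-to-dosing interval: 90 + 1 = 91 to 92 + 14 = 106 days.
- Part not covered by the 30-day rule: 91 − 30 = 61 to 106 − 30 = 76 days.

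So there are about 61 to 76 days in which a compliant subject could be biopsied while on estrogen.

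**3. Size if fulvestrant has no effect.** Let k of 24 subjects stop estrogen between biopsy and dosing, and let each have a w% fall in Ki67 from that alone. The spurious mean fall is (k/24) × w. Neither k nor w is in the documents. The ranges k = 2 to 6 and w = 10 to 47.4 are assumptions; 47.4 is borrowed from the 250 mg arm quoted in Section 5.0, which is a drug response and not an estrogen-withdrawal response.

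- Low: 2/24 × 10 = 0.8 points.
- High: 6/24 × 47.4 = 11.9 points.

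**4. Size if fulvestrant works as anticipated.** Suppose the effects multiply and fulvestrant halves what remains. An exposed subject's total fall is 1 − 0.5 × (1 − w) = 0.5 + 0.5w, with w as a fraction, so the excess over 50% is 0.5w. The mean excess is half of the figures in step 3.

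- Low: 0.8 × 0.5 = 0.4 points.
- High: 11.85 × 0.5 = 5.9 points, and 5.9/50 is about 12% of the anticipated decline.

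**5. Effect on the test.** Take k = 6, w = 40 and no fulvestrant effect. The spurious mean is 6/24 × 40 = 10 points. With SD² = s² + 0.25 × 0.75 × 40², the two-sided rejection probability is 8.5% for s = 83.7 and 9.7% for s = 72.3, against a nominal 5%. With k = 2 and w = 20 it is 5.1%.

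**6. Precision of a restricted analysis.** Same power method, detectable effect size at 80% power:

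| n | detectable effect size | power at d = 0.597 |
|---|---|---|
| 24 | 0.60 | 80% |
| 22 | 0.63 | 76% |
| 20 | 0.66 | 72% |
| 18 | 0.70 | 67% |

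**The case against.** **The baseline tissue may be recent.** Section 9.2 and Table 2 list a pathological assessment in the baseline window, and Sections 9.1 and 9.2 accept earlier tests only if done within 2 weeks before participation or enrollment. Read literally, baseline tissue would date from about Day −28 at the earliest (14 + 14 days), inside the estrogen-free period. That would remove the on-estrogen baseline. But no baseline biopsy procedure is described, and Section 13.2 names the diagnostic biopsy. Even a new biopsy on Day −14 could fall only 16 days (30 − 14) after estrogen was stopped. This shows a conflict to be resolved; it does not close the gap.

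**The 3-month limit concerns ER positivity, not Ki67.** True. The link is that Section 13.2 uses the diagnostic biopsy as the Ki67 baseline, and no separate age limit for that tissue is given.

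**There may be no such subjects.** This stands. The documents permit the case but do not show that any is expected.

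**The mechanism is assumed.** This stands too. Section 5.0 reports that fulvestrant lowers Ki67 more at the higher dose. It does not say that stopping exogenous estrogen lowers Ki67. The direction is a reasonable inference, not a premise of the protocol.

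**The rule is not in the exclusion list, so a reader might infer that it goes unchecked.** The documents do not support that. Section 9.10 applies before dosing, and medical history and concomitant medications are collected at baseline. What can be said is that Sections 9.10 and 8.1.2 do not match.

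**Ki67 is not the primary objective.** Correct. Safety and PK conclusions do not depend on this point.

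**Conclusion.** The gap is in the text: a compliant subject can have an on-estrogen baseline and an off-estrogen surgical value, and the uncontrolled paired analysis of Ki67, ER and PgR can then attribute the effect of stopping estrogen to fulvestrant. Its size is unknown. Under the assumed ranges it is 0.8 to 11.9 points with no fulvestrant effect, and about 0.4 to 5.9 points if fulvestrant halves what remains.

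Two stronger readings are tempting. One is that estrogen withdrawal *is* being counted as drug effect; the documents support only that it *can* be. The other is that about a quarter of the anticipated 50% decline could be artifact (11.9/50). That sets a figure valid only when the drug does nothing against a decline that assumes it works; on the multiplicative assumption the upper end is about an eighth.

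This is an inexpensive improvement to how the marker results can be interpreted, not a flaw in the primary safety assessment.

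**What to change.** 1. Record, for every subject, estrogen use and its stop date relative to the biopsy that supplies baseline Ki67, ER and PgR.
2. In the SAP, before database lock, pre-specify a Ki67/ER/PgR analysis limited to subjects with no estrogen therapy in the 30 days before that biopsy, reported beside the all-subject analysis. Any claim of a fulvestrant effect on these markers should require the two to agree. Define agreement in advance through the estimates and 95% intervals; requiring significance in both would be hard to meet in the smaller set.
3. Leave the safety and PK sets unchanged.
4. Reconcile Section 9.10 with Section 8.1.2 on estrogen therapy. Reconcile the baseline pathological assessment in Section 9.2 and Table 2 with the diagnostic-biopsy baseline in Section 13.2.

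Making the restricted set the main analysis is debatable and is not needed; reporting both keeps all 24 subjects.

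**Cost.** Possibly one CRF field, since the baseline collection of history and medications is not shown to capture stop dates relative to the biopsy. The restricted set is less precise, as the table in the working shows, and Section 8.4 replaces only subjects who withdraw before surgery, so subjects outside the restricted set would not be replaced. If nobody was exposed, the two analyses coincide and nothing is lost.

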### 9.11 Pain Assessment

Obtain Pain Assessment (see Appendix B), minimally, according to the following schedule

Visit	Collection Time
Day of Fulvestrant Administration (Day 0)	
 
• Prior to fulvestrant administration and prior to nipple preparation for intraductal subjects
 
• Post Nipple Anesthetic (Intraductal Subjects Only)
 
• At completion of fulvestrant administration/instillation
 
• 30 minutes post administration
 
• 1 hour post administration
 
• 4.5 hours post administration
 

Day +7±2	Any time during visit
Pre-Operative (Day 14 ± 7)	Any time during visit

If, during intraductal fulvestrant infusion, the subject reports Grade 3 or 4 pain (CTCAE criteria) in the breast which does not resolve within 10 minutes after infusion of the drug, treatment of additional ducts will be discontinued. Blood draws and follow-up assessment as well as pathological assessment as described in Section 10.1 will be performed per the protocol.

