## **7.0 TRIAL DESIGN**

This is an open-label, non-randomized pharmacokinetic study of pre-surgical fulvestrant in women scheduled for mastectomy or lumpectomy. Eligible subjects will be identified upon admission to the institution for surgical management of breast cancer or DCIS, specifically mastectomy or lumpectomy. There will be 5 groups, each consisting of 6 subjects. The first subject of each group will receive fulvestrant administered intramuscularly and the next 5 subjects will receive fulvestrant intraductally. Subjects where at least 1 suitable duct is identified may undergo nipple aspiration in order to facilitate duct identification and

intraductal infusion of a fulvestrant accompanied by imaging (saline+ ultrasound). A maximum of 5 ducts will receive intraductal infusion of fulvestrant. Across all ducts, the total dose will not exceed 500 mg (10 mL). All subjects will be monitored for systemic and local adverse events during the procedure, immediately following the procedure, within 30 minutes, 1 hour, 4 hours and by phone following discharge on Days +1 and +2, +7, and pre-operative. Subsequent to mastectomy or lumpectomy, subjects will be assessed for systemic adverse events until discharge. Per schedule specified in Table 1, subjects will undergo serial blood draws to determine fulvestrant blood concentration levels.

When fulvestrant is administered at or below the dose level of 500 mg currently in routine clinical use, emergence of Dose Limiting Toxicities (DLT) is unlikely, but not impossible.

Since only a single instillation of fulvestrant is given in this protocol, dose reduction in individual subjects is not possible. However, if any of the DLT parameters reaches any of the thresholds values set in Section 10.3 the dose in subsequent subjects will be reduced to 250 mg (one 5 mL vial).

The purpose of this observational study is to understand the safety and tolerability of giving the anti-estrogen drug fulvestrant directly into the milk ducts of the breast, and collect any evidence of pathologic response. This study will be conducted under good clinical practice (GCP) guidelines as outlined in Section 15.5 Good Clinical Practice. This will be a single-dose study with two treatment groups: 500 mg administered intramuscularly (n=6) and up to 500 mg administered intraductally (n=24).

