### 9.3.4 Post Fulvestrant Administration and Pre-Surgery Assessment

After fulvestrant administration has been completed, subjects will be assessed for local and systemic adverse events during, immediately after and at 30 minutes, 1 hour and 4 hours. As noted above, **subjects must have at least 14 days between fulvestrant administration and surgery, but no longer than 45 days.** Pre-operative assessment, as described below, will occur before the subject undergoes mastectomy or lumpectomy 14 days following intraductal therapy, unless medical condition prohibits operative management. Subjects will complete a pain assessment at completion of fulvestrant administration, then at 30 minutes, 1 hour, and 4.5 hours until discharge from the clinic. Following discharge, the site trial staff may assess for AEs by phone. Subjects will be assessed for pain, AE, ECOG performance scale (Appendix A), blood drawn per drug schedule and vital signs (blood pressure, respiratory rate, pulse, temperature) recorded. See Table 2 to determine daily requirements for study procedures.

Subjects participating in this clinical trial will undergo either a mastectomy or lumpectomy. Notwithstanding the unlikely occurrence of an AE that affects the surgery date, participation in this trial does not alter the scheduled surgical management of mastectomy/lumpectomy or date. In order for subjects to undergo surgery, Atossa recommends but does not require the following requirements be met:

- ECOG performance scale of 0-2
- Stable vital signs (pulse, blood pressure, respiratory rate and temperature)
- Adequate organ function as determined by:
  - Absolute neutrophil count (ANC)  $\geq 1500/\mu\text{L}$
  - Platelets  $\geq 100,000/\mu\text{L}$
  - Hemoglobin  $\geq 9.0 \text{ g/dL}$
  - Creatinine  $\leq 2$  times upper limit of normal
  - Bilirubin  $\leq 2$  times upper limit of normal
  - Transaminases (AST/SGOT and ALT/SGPT)  $\leq 2.5$  times upper limit of normal

The surgeon may elect to postpone the surgery if adverse events may compromise patient

safety. In the event this occurs, subjects will be treated to abate adverse events prior to surgery. They will remain in the clinical trial and be included for analysis.

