### 11.2 Safety Monitoring and Reporting

#### 11.2.1 Adverse Events

Both signs and symptoms of local (breast and chest wall) and systemic toxicity will be evaluated.

The most common side effects of fulvestrant when given into the muscle in the buttocks, reported from previous studies and after marketing, include:

- nausea (14%)
  - injection site pain (12%)
  - back pain (11%)
  - bone pain (9%)
  - headache (8%)
  - joint pain (8%)
  - pain in extremities (7%)
  - hot flash (7%)
  - weakness (6%)
  - vomiting (6%)

- loss of appetite (6%)
- muscle pain (6%)
- constipation (5%)
- cough (5%)
- shortness of breath (5%)

Increased liver enzymes (which may indicate liver damage) and allergic reaction may also occur, but in less than 5% of patients who receive the drug.

All of the side effects listed above may occur, but may or may not be the same in severity or frequency when fulvestrant is injected into the breast.

There are additional possible discomforts or risks from administration into the breast, as that process includes administration of anesthetic, breast duct identification using the aspirator, catheter placement and fulvestrant injection. These additional risks include:

- injury to the milk duct
- bleeding and bruising
- infection
- breast pain, discomfort or inflammation
- allergic reaction to the anesthetic, ~~eyes~~, or the study drug, fulvestrant, used in this study.

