### 11.2.2 Adverse Event (AE) Definition

An adverse event (AE) is defined by the NCI as any unfavorable symptom, sign, or disease (including an abnormal laboratory finding) associated with the use of a medical treatment, device or procedure that may or may not be considered related to or caused by the medical treatment or procedure. An AE also includes any newly occurring event or previous condition that has increased in severity or frequency since the initiation of the investigational procedures or administration of the investigational drug or device.

Assessment of the occurrence of an AE will be based on changes in the subject's laboratory results and/or signs and symptoms. AEs will be monitored until they are resolved or clearly determined to be due to a subject's stable or chronic condition or concurrent illness (es). Medical care will be provided, as defined in the informed consent, for any AE.

Collect all Adverse Events on the Adverse Event (AE) CRF and the MedWatch 3500 form. There are two types of adverse events, expected and unexpected. It is expected that subjects may feel slight minimal discomfort during the study procedures and post-procedure; both events are considered self-limiting. It is further expected that subjects will experience post-operative discomfort after surgery. This will be treated according to routine institution and clinician routine. Subjects who experience any untoward or unexpected after-effects following the study procedures, blood collection or surgery are instructed to contact the Principal Investigator or study coordinator immediately.

All AEs, regardless of intensity or causal relationship, are to be recorded in the CRF and source documentation. The investigator must determine both the intensity of the AE and the event's relationship to study product administration. Unexpected events such as excessive

discomfort or prolonged breast pain following the procedure, infection, persistent discharge, or any other condition reported by the subject and treated by a physician should be reported on the AECRF.

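### Pain is a named primary-endpoint measure, yet no 0-10 score is required from 4.5 h after dosing until Day 5-9; the existing Day 1 and Day 2 contacts could supply one cheaply

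*Combined protocol and SAP*

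**What the plan says.** Section 13.2 defines the endpoint: "The primary endpoint of this study is to assess safety and tolerability as measured by adverse events, subject pain assessment", together with signs of irritation on the excised specimen. Pain assessment thus stands beside adverse events and is not part of them.

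Section 9.11 gives the timetable: "Obtain Pain Assessment (see Appendix B), minimally, according to the following schedule". It lists time points on Day 0 ending at 4.5 h, then the Day 7±2 visit, then the pre-operative visit. Table 2 matches: the pain row is marked on Day 0, Day 7 and pre-op, and is blank for Days 1 and 2.

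Contacts on Days 1 and 2 are nevertheless planned. Section 7.0 has subjects monitored for adverse events "by phone following discharge on Days +1 and +2, +7, and pre-operative". Section 9.4 begins "The following procedures will be performed on Days 1 and 2 post fulvestrant administration" and lists two items, concomitant medications and adverse events, with phone allowed. Section 9.3.4 says in general terms that subjects are assessed for pain, but it names no day and sends the reader elsewhere: "See Table 2 to determine daily requirements for study procedures".

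Appendix B is a 0-10 scale that may be answered verbally. It names no body site.

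**The concern.** Section 11.2.1 lists "breast pain, discomfort or inflammation" among the additional risks of giving the drug into the breast. Characterising the tolerability of that route is the trial's primary aim, and one of its named measures is the subject's own pain rating. In the first days after the procedure no such rating is required, although staff are already due to evaluate the subject twice.

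Intraductal subjects also receive a nipple anesthetic before instillation, so all their post-dose scores on Day 0 follow it. The documents do not say how long it acts. The first score required outside that setting comes at Day 5 to 9. Any description of pain over time on the 0-10 scale, or any qualitative comparison of the two routes on that scale, has nothing required in between. At stake is the completeness of one descriptive measure.

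**Working it through.** The plan gives no figure for this point. Its only power statement concerns Ki67 (Section 13.2: 24 intraductal subjects, effect sizes 0.60 and 0.69). That reproduces at 80.4% and 89.9% with a paired t-test at two-sided 5% (an assumed level, since none is stated), and it does not depend on the pain schedule. The check here is of the schedule.

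**Do the schedules agree?** Sections 9.4, 9.5 and 9.11 and Table 2 all give the same picture: no pain score on Days 1 and 2, and a score at Day 7±2. The blank in Table 2 is therefore not an accident of table layout.

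**Inputs.** Last Day 0 score: 4.5 h (Section 9.11; Table 2, footnote 6). Next required score: Day 5 to 9 (Section 9.5). Assumptions: each day counts as 24 h from dosing, and the Day 1 and Day 2 contacts fall at 24 h and 48 h.

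**Present gap** = 24 × visit day − 4.5 h:
- Day 5: 120 − 4.5 = 115.5 h
- Day 7: 168 − 4.5 = 163.5 h
- Day 9: 216 − 4.5 = 211.5 h

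**Scheduled scores per subject.**
- Intraductal: 6 on Day 0 + Day 7 + pre-op = 8.
- Intramuscular: 4 or 5 on Day 0 + 2 = 6 or 7. The doubt comes from footnote 6 of Table 2, "Pain Assessment completed prior to fulvestrant administration/nipple preparation (Intraductal only", which can be read as making the pre-dose score intraductal only; Section 9.11 reads more naturally as requiring it in both groups.
- Falling on Days 1 to 4: none in either group, against two planned contacts.

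**With a score at both contacts.**
- First score after discharge: about 24 h, instead of 120 to 216 h.
- Required scores between discharge and surgery: from 2 to 4.
- Longest remaining gap, from Day 2 to the Day 7±2 visit: 120 − 48 = 72 h, 168 − 48 = 120 h or 216 − 48 = 168 h. As a share of the present gap: 72/115.5 = 62%, 120/163.5 = 73%, 168/211.5 = 79%.
- Added scores: 2 per dosed subject. With 24 intraductal and 6 intramuscular subjects (Section 13.2), 48 + 12 = 60. With five groups of one intramuscular and five intraductal subjects (Section 9.1), 50 + 10 = 60. Either figure assumes exactly 30 dosed subjects. Section 8.0 says at least 30, and Section 8.4 replaces withdrawals before surgery, so the total can be higher.

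**The case against.** The strongest reply is that this is a preference about sampling frequency. The schedule is internally consistent, gives intraductal subjects eight scores, and is expressly a minimum. The days in question are covered by another component of the same endpoint: Section 11.2.2 states "All AEs, regardless of intensity or causal relationship, are to be recorded in the CRF and source documentation", asks that prolonged breast pain go on the adverse event form, and tells subjects to report unexpected after-effects at once. Analgesic use can be seen through concomitant medications. The rule for stopping infusion (Section 9.11) and the dose-limiting toxicity rule (Section 10.3) use adverse event grades, never the 0-10 score. Section 13.2 sets out no pain summary by time point, and Section 13.0 leaves further detail to a later analysis plan.

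Most of this stands, and it is why the point is no more than a suggestion. Two things remain. A minimum permits extra scores but requires none, so optional scores would come unevenly. And an investigator's adverse event grade is not the subject's own 0-10 rating, so it cannot be joined to the Day 0 and Day 7 scores on one scale.

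Section 9.3.4 uses permissive wording about phone follow-up after discharge, which might suggest that the contacts are optional. Sections 7.0 and 9.4 and Table 2 schedule the evaluations; the choice left open is whether to use the phone.

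A reader might infer that pain goes unobserved for about a week, or that the trial misses the peak. The documents support neither. Adverse event evaluation covers the period, and nothing in them says when pain after instillation peaks or how long it lasts.

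**Conclusion.** The point holds as a low-cost improvement to how the trial measures its own tolerability endpoint. It is not an error or an inconsistency in the plan. No Appendix B score is required for 115.5 to 211.5 h after the last Day 0 score, although two evaluations are scheduled in that time. What is missing is the score, not all information on pain.

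The benefit is modest and cannot be quantified from the documents, because they give no time course for pain. It would be wrong to conclude that the primary endpoint cannot be assessed or that dose decisions are weakened: adverse events are collected throughout, and no dose rule uses the score. Sample size, power and the Ki67 analysis are unaffected. The hour counts rest on 24-hour days from dosing and on contacts at about 24 h and 48 h.

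**What to change.** Add the Appendix B 0-10 score to the Day 1 and Day 2 contacts in Section 9.4, Section 9.11 and the pain row of Table 2, taken verbally by phone where needed. Word the question exactly as at the other time points. If a score specific to the treated breast or the injection site is wanted, add it at every time point: site-specific wording at two contacts only would not be comparable with the other scores.

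The cost is one extra question at each of two existing contacts, one CRF field per contact and the text edits, with no new visit or staff. The interval from Day 2 to the Day 7±2 visit stays unscored.
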